#### 4.7 Alert Notification

Primary care providers will be notified of clinically significant findings identified at study follow-up visits.

#### **4.8 Strategies to Promote Adherence and Retention**

We will employ a number of retention strategies during the study to promote attendance of subjects in both groups at all follow-up visits. These include a highly trained, competent and consistent staff, flexible scheduling, readily available mass transit, reimbursement for parking on-site, and reimbursement of \$50 for measurements completed at baseline and 24 months, and \$25 at 6, 12, and 18 months. All families will understand that this is a two-year commitment and we will not enroll families who are unable or unwilling to commit for the entire period. If families unexpectedly move out of the region during the study period, we will make every effort to continue their participation to the measurement visits by compensating for travel costs. Operations will be geared to ease scheduling of the measurement visits and to ensure the comfort and enjoyment of the subjects and parents during all measurements. The schedule of contacts is designed to facilitate participant retention through regular contacts. Parents will be asked to provide contact information for individuals (relatives, friends, co-workers) who would likely know their location in the event the child becomes lost to follow-up. This contact information will be stored locally in a secure location.

#### **4.9 Unscheduled Visits**

We will ask participants to notify the study team of any unscheduled visits to their primary care providers or other health care settings for diagnosis and management of urinary tract infections. We will also inquire about and document unscheduled visits to healthcare providers for urinary tract symptoms or infection at the time of the bimonthly phone calls.

#### **4.10 Subject Completion/Withdrawal**

Criteria for withdrawal of subjects and plans for provision of care after withdrawal. Example: Subjects may withdraw from the study at any time without prejudice to their care. They may also be discontinued from the study at the discretion of the Investigator for lack of adherence to study treatment or visit schedules or AEs. Children who are started on antimicrobial prophylaxis will continued to be followed for the duration of the study period but they will not contribute data to analyses after prophylaxis is begun. The Investigator may also withdraw subjects who violate the study plan, or to protect the subject for reasons of safety or for administrative reasons. It will be documented whether or not each subject completes the clinical study. If the Investigator becomes aware of any serious, related adverse events after the subject completes or withdraws from the study, they will be recorded in the source documents and on the CRF.

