##### **4.10.1 Early Termination Study Visit**

List the procedures that will be performed for each subject that withdraws prior to completing the study. Example: Subjects who withdraw from the study will have all procedures enumerated for the 24 month visit as the early termination visit.

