## 7.2 Scheduling of Follow-up Contacts

Follow-up procedures will continue for each participant until their end-of-study visit at 24 months after enrollment, regardless of designation of treatment failure.

Project Coordinators should always remind parents/guardians that routine follow-up consists of both clinic visits and interim telephone interviews, which are scheduled every 2 months. At the enrollment and baseline visit, the Coordinator should schedule the next two telephone contacts, at 2 and 4 months from enrollment. At the end of every follow-up contact, the next 2 contacts should be confirmed or scheduled with the parent/guardian.

When scheduling clinic visits, the Coordinator will always need to verify that the principal investigator or his/her designee (which may be the Coordinator) is available to perform any necessary examinations during scheduled contacts.

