#### **7.4.6 The End-of Study Follow-up Clinic Visit**

Follow-up procedures continue for a two-year period after enrollment, regardless of whether or not potential endpoints occur,, or the participant is deemed a treatment failure.

The end-of-study follow-up clinic visit should take place during the 24th month of follow-up (contact occasion 13). Concerted effort should be made to obtain the required clinic data regardless of how well a participant's previous participation has been, including those participants who are on telephone contact only, and including participants who have dropped out of the study. Without complete assessment of study endpoints, the scientific validity of the entire study may be compromised.

The end-of-study visit includes the same procedures described above (section 7.4.4) for follow-up clinic visits, but also includes:

- DMSA scans, assessing new or worsening renal scarring. Refer to Chapter 3: Radiology.
- The self administered questionnaires, LIA Questionnaire (LIQ) and DV Questionnaire (DVQ) are administered. Refer to chapter 4: Enrollment and Baseline, section 4.5.3.
- Blood and urine collection. Refer to Chapter 5: Specimen Collection and Processing.

Refer to Table 7.3 for the required data collection forms at this visit.

If a participant has been on telephone-contact-only, special efforts should be made to try and get the participant and parent/guardian in for this last clinic visit. If the participant has previously dropped out of the study, but has not refused consent, a final effort should be made to have the participant and parent/guardian come in for this exit clinic visit.

At the final routine clinic visit the participant and their family will be given a certificate of appreciation or a commemorative token for his or her 2-year commitment to the CUTIE study.

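### Protocol 4.10 lets the investigator end a child's follow-up for non-adherence, plan violations or administrative reasons, contradicting the MOP, which keeps seeking outcome data unless consent is refused

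*Protocol*

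**What the plan says.** Protocol 4.10 (Subject Completion/Withdrawal) opens with an unfilled template prompt and the label Example. It then allows a child to be "discontinued from the study at the discretion of the Investigator for lack of adherence to study treatment or visit schedules or AEs". Later in the same paragraph: "The Investigator may also withdraw subjects who violate the study plan, or to protect the subject for reasons of safety or for administrative reasons".

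Protocol 4.10.1 (Early Termination Study Visit), also introduced by a template prompt and the label Example, says: "Subjects who withdraw from the study will have all procedures enumerated for the 24 month visit as the early termination visit". Table 1 lists a DMSA scan at the 24-month visit.

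The Manual of Procedures (MOP), bound in the same document, reads differently:

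- MOP 7.2: "Follow-up procedures will continue for each participant until their end-of-study visit at 24 months after enrollment, regardless of designation of treatment failure".
- MOP 7.4.6, on the end-of-study visit: "Concerted effort should be made to obtain the required clinic data regardless of how well a participant's previous participation has been". It extends this to families on telephone contact only, "including participants who have dropped out of the study", and warns that incomplete endpoint assessment could undermine the validity of the whole study.
- MOP 7.8.1, 7.9.1 and 7.10 provide telephone-only follow-up and recovery of dropouts.
- MOP 7.9.8: data collection stops when consent is refused.
- MOP 8.3: CUTIE has no study medication.

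**The concern.** The two rules point in opposite directions for the same child. A child who misses visits may be discontinued under Protocol 4.10 but must be pursued for outcome data under MOP 7.4.6. In an observational cohort without a study drug, non-adherence gives no treatment-related reason to stop observing.

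Two endpoints are exposed. The primary endpoint (Protocol 5.1 and 5.2) is any scar on the outcome DMSA, planned for 24 months after the index UTI. A secondary endpoint is the proportion with at least one recurrent UTI, which can be counted only while contact continues. Poor attendance could go with later detection or treatment of UTI, and so with scarring. If it does, discretionary discontinuation makes the missing outcomes informative, to a degree that may vary with each site's habits. The document gives no data on that link, so it is a plausible risk and not a shown effect.

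**Working it through.** **1. The passages side by side**

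| Situation | Protocol 4.10 / 4.10.1 | MOP |
|---|---|---|
| Missed visits | Investigator may discontinue; 24-month procedures at exit | End-of-study data still sought (7.4.6); telephone contact may replace visits (7.8.1, 7.9.1) |
| Non-adherence to study treatment | Investigator may discontinue | No study medication exists (8.3) |
| Violation of study plan; administrative reasons | Investigator may withdraw | No such ground in Chapter 7 |
| Dropout | 24-month procedures at exit | Recovery attempted (7.10); exit visit sought (7.4.6) |
| Consent refused | Free to withdraw at any time | Data collection stops (7.9.8) |

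The second to fourth rows of Protocol 4.10 cannot be dismissed as wholly unedited boilerplate. The same paragraph holds a sentence written for this study, on children who start antimicrobial prophylaxis, so a site could reasonably treat the whole section as operative.

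**2. The plan's own figure, and whether power is the issue**

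Inputs (Protocol 6.2, Table 8): scarring p = 0.15 in both groups, margin 0.10, one-sided alpha 0.05, power 80%, ratio 150:360 (r = 2.4).

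n in group A = (1.645 + 0.842)² × 0.15 × 0.85 × (1 + 1/2.4) / 0.10² ≈ 111.7, rounded up to 112. Group B is 112 × 2.4 = 268.8. The total is 381, against 380 in Table 8, so the figure reproduces.

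For the same one-sided test, power is Φ(0.10/SE − 1.645) with SE = √(0.1275/n_A + 0.1275/n_B):

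- 150 + 360, no loss: 89%
- 10% lost in total (135 + 324): 86%
- 10% lost per year (121.5 + 291.6): 83%

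The attrition already allowed for leaves this test above 80%. The question is therefore bias, not power.

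**3. Illustration of the bias**

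Let f be the share of CUTIE children discontinued with no outcome, and k their scarring rate relative to the overall rate p = 0.15. Neither f nor k is in the documents; both are assumptions.

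Retained rate = (p − f·k·p)/(1 − f).

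| f (children of 360) | k = 1 | k = 2 | k = 3 |
|---|---|---|---|
| 5% (18) | 15.0% | (0.15 − 0.015)/0.95 = 14.2% | (0.15 − 0.0225)/0.95 = 13.4% |
| 10% (36) | 15.0% | (0.15 − 0.030)/0.90 = 13.3% | (0.15 − 0.045)/0.90 = 11.7% |

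The fall is 0 points at k = 1, 0.8-1.6 points at f = 5%, and 1.7-3.3 points at f = 10%, for k from 2 to 3. If k were below 1 the retained rate would rise instead. The 18-36 children are 18/510 = 3.5% to 36/510 = 7.1% of the planned total of 510.

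**The case against.** The strongest reply is Protocol 4.10.1: a child who withdraws is to have the 24-month procedures at exit, and those include a DMSA. On that text the scarring outcome is taken early rather than removed. A reader might infer from 4.10 alone that it strips out outcomes; 4.10.1 means the documents do not support that. The safeguard is nevertheless weak, for four reasons:

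- It too is unfinished template text, and it speaks of subjects who withdraw.
- Families who have been missing visits may not attend an extra one.
- An early scan is not the 24-month endpoint. Under Protocol 6.1.2 an earlier scan becomes the primary outcome if it was indicated and shows scarring; a clean early-termination scan has no stated role.
- No exit scan restores later recurrent UTIs.

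The other replies also have weight. Section 4.10 is permissive, Protocol 4.8 aims at retention, and MOP Chapter 7 (October 2008) postdates the protocol chapter (April 2008), so sites may simply follow the MOP. The sentence in MOP 7.2 is qualified by treatment failure and does not itself address poor attendance. The conflict therefore rests mainly on MOP 7.4.6 and 7.9.8. The MOP asks for concerted effort and recognises loss to follow-up; it does not promise a scan for every child. These points limit how often the conflict will bite, but leave two incompatible rules in one document.

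**Conclusion.** The contradiction holds and should be corrected. Applied as written, Protocol 4.10 would lose or truncate the 24-month DMSA and recurrent-UTI ascertainment, on grounds that may relate to outcome.

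The size is conditional. It is zero if loss is unrelated to scarring. It is 0.8-3.3 points off the observed CUTIE rate if 5-10% of children have no outcome at all and scar at 2-3 times the 15% rate. Any scans obtained under 4.10.1 would change that figure.

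A reader might go further and infer that the rule biases the no-VUR group alone, or that it pushes the study towards a false finding of equivalence. The documents support neither. RIVUR's withdrawal rules are not given, and the introduction says CUTIE took its documentation from RIVUR, so a similar rule may apply to the placebo group and the effect on the difference is unknown. If only CUTIE were affected and the true rates were equal, a lower CUTIE rate would widen the gap and make equivalence harder to show.

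**What to change.** 1. In Protocol 4.10, delete the template prompt and the reference to study treatment. Remove non-adherence, violation of the study plan and administrative reasons as grounds for ending follow-up.
2. State there, in line with MOP 7.4.6 and 7.9.8, that none of these ends outcome ascertainment: contacts and the outcome DMSA continue to be sought, and withdrawn consent is what stops data collection. Require the reason for each missed contact to be recorded.
3. Replace the template text in Protocol 4.10.1 with study-specific wording that matches.
4. The AE and safety clauses in 4.10 also need reconciling with the MOP. How those situations are managed is for the study team, and no rule is proposed here.

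The cost is protocol wording. The MOP already prescribes the follow-up, so no new procedures are added.

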##### **4.10.1 Early Termination Study Visit**

List the procedures that will be performed for each subject that withdraws prior to completing the study. Example: Subjects who withdraw from the study will have all procedures enumerated for the 24 month visit as the early termination visit.

### **5 STUDY ENDPOINTS AND EVALUATIONS**

#### **5.1 Overview of Primary and Secondary Endpoints**

The proportion of children who have any renal scars assessed on the outcome DMSA scan will serve as the principal analysis variable. Secondary endpoints include the proportion of

children with severe scarring, the proportion of children who have at least one recurrent UTI, and the proportion of children who become "treatment failure".

## 5.2 Primary Endpoint: Renal Scarring

The incidence and extent of renal scarring will be determined 24 months after the index UTI episode using renal scintigraphy ( $^{99}\text{Tc}$  dimercaptosuccinic acid (DMSA) scan). Children who experience "treatment failure" as defined in the parent study will have the outcome scan approximately 4 months later. Renal scarring will be defined as decreased uptake of tracer associated with loss of contours or cortical thinning. In order to quantify the extent of renal scarring, each kidney will be divided into 12 segments and a five level grading system will be applied (Figure 6). Severe scarring will be defined as the presence of grades 3 or 4 scarring on at least one kidney.

## 5.3 Secondary Endpoints

### 5.3.1 Recurrence of UTI

Suspected recurrent UTI events will be reviewed and adjudicated to determine if they meet the RIVUR criteria for a secondary endpoint. The definition of recurrent  $F/S$ UTI requires the presence of (1) fever or urinary tract symptoms, and (2) pyuria based on urinalysis, and (3) culture-proven infection with a single organism. A UTI will be defined as recurrent only if its onset occurs more than 2 weeks from the last day of treatment for the preceding UTI, or following a negative urine culture.

### 5.3.2 "Treatment Failure"

Although treatment will not be provided as part of this observational study protocol, we will characterize the children in this ancillary study in terms of the criteria used to define treatment failure in the RIVUR study. In any participant, the occurrence of two  $r$ UTIs or a total of four  $F/S$ UTIs during the study period or an interim 12-month scan showing new scarring at a site different from the index APN or worsening scarring evidenced by extension of a preexistent scar seen on the baseline DMSA scan will be classified as a treatment failure. In treatment failure cases where new or worsening scarring is observed on the 12-month DMSA scan, the interim scan may serve as the outcome DMSA scan. Children whose baseline DMSA scan shows grade 3 or higher scarring in either kidney will have a repeat DMSA performed at the time of any recurrent  $r$ UTI. If additional renal segment involvement is observed in comparison with the baseline scan, these children will also be categorized as treatment failure and have an outcome DMSA scan at approximately 4 months following the  $r$ UTI. If no further damage is apparent, they will continue in the study as assigned.

Children whose interim 12-month scan shows new or worsening scarring in comparison to a previous scan will be classified as meeting treatment failure criteria. The interim scan will serve as the outcome DMSA scan in these participants.

---

 Must occur within  $\pm$  24 hours of initiating work-up for UTI.

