Chronic constipation in the toilet trained child, as defined by the Paris Consensus on Childhood Constipation Terminology (PACCT) Group 	
The occurrence of 2 or more of the following during the last 8 days in the toilet-trained child
 
 
• Frequency of bowel movement <math>< 3</math> / week
 
• More than one episode of fecal incontinence / week
 
• Large stools in the rectum or palpable on abdominal examination
 
• Passing of large stools that may obstruct the toilet
 
• Display of retentive posturing and withholding behaviors
 
• Painful defecation
 

Treatment failure:	
Treatment failure is defined by:
 
I. In any participant:

---

- Occurrence of 2 recurrent  $\text{F}_{\text{UTI}}$ s or a total of 4 recurrent  $\text{F}_{\text{SUTI}}$ s within the study period, OR
- Interim 12-month scan shows new or worsening scarring at a site different from the index APN or worsening scarring evidenced by extension of a preexistent scar seen on the baseline DMSA scan (note, the interim scan may serve as the outcome DMSA scan in these participants).

OR

- II. In children with baseline scarring grade 3 or higher:
  - Children whose initial DMSA scan shows grade 3 or higher scarring in either kidney will have a repeat DMSA performed at the time of any recurrent  $\text{F}_{\text{UTI}}$ ; if additional renal segment involvement is observed (APN or scar) compared with the baseline scan, then the child will be categorized as treatment failure and have an outcome DMSA scan at approximately 4 months following the  $\text{F}_{\text{UTI}}$ . If no additional renal segment involvement is observed, the child will continue in the study as assigned.

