Instead of VUR, the common denominator in all cases of post-infectious renal scarring appears to be inflammatory response to acute infection of the renal parenchyma. Using serial DMSA renal scans, investigators have observed that acute DMSA renal scan defects can persist as renal scarring in infected kidneys and that the sites of new renal scarring correspond exactly to those sites of acute pyelonephritis seen on the initial DMSA renal scans. Contralateral normal kidneys and initially uninvolved areas of abnormal kidneys almost always remain normal on follow-up DMSA renal scans. These observations provide convincing clinical evidence that renal parenchymal infection, rather than VUR, is the prerequisite for acquired (postnatal) renal scarring. Once bacteria have invaded the renal parenchyma, the inflammatory response appears similar and the propensity for renal scarring is equally as great whether or not VUR is present.

Despite these findings, the importance of VUR (particularly Grades III or higher) as a risk factor for renal scarring should not be completely discounted. Clearly, children with moderate and severe reflux are much more likely to develop acute pyelonephritic damage than children with mild or no reflux. Furthermore, although 62 per cent of the kidneys with post-pyelonephritic renal scarring in one study were drained by nonrefluxing ureters, renal scarring was still significantly more common in those kidneys with Grade III or higher VUR compared with kidneys with mild or no reflux. Thus, the increased propensity for scarring in children with higher grades of VUR is attributable in part to the increased risk of these kidneys for acute inflammatory damage at the time of the initial infection. Indeed, in one study that attempted to quantitate the area of acute pyelonephritic parenchymal damage, the presence of grade  $\geq 3$  reflux was associated with a significantly greater frequency of kidneys demonstrating large defects (defined as  $>10$  per cent of the kidney demonstrating DMSA uptake  $<2$  SD of the control kidney) when compared to kidneys with no VUR ( $p < 0.02$ ). Thus, when present, moderate or severe reflux (grade  $\geq 3$ ) remains the most significant host risk factor for acute pyelonephritis and renal scarring.

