#### 4.5 Outcome DMSA Scan

Outcome DMSA renal scans will follow the same procedures and standards of the baseline scan. In general participants will have the outcome DMSA scan performed 24 months after the index UTI. For safety reasons, we will use the criteria developed to define treatment failure for the RIVUR study as indications for performance of an early DMSA scan. Therefore, children whose baseline DMSA scan shows minimal or no scarring (grade 2 or less in each kidney) will have their outcome DMSA scan performed early if they experience the occurrence of 2 recurrent  $\neq$ UTIs or a total of 4 recurrent  $\neq$ UTIs within the study period. The outcome DMSA in these children will be performed approximately 4 months after the last UTI that qualified them as a "treatment failure". Children whose baseline DMSA scan shows grade 3 or higher scarring in either kidney will have a repeat DMSA scan performed at the time of any recurrent  $\neq$ UTI; if additional renal segment involvement (acute pyelonephritis or renal scarring) is observed, then, an outcome DMSA scan will be performed at approximately 4 months following any  $\neq$ UTI. If no additional renal segment involvement is observed, the child will have the outcome DMSA scan performed at 24 months per routine. Finally, children who have a febrile UTI in the first 8 months of the study will have an interim DMSA scan performed at 12 months. If new renal scarring is noted, that child will be considered a treatment failure and the interim DMSA scan will serve as the outcome scan. If a febrile UTI occurs within 8-12 months, the interim DMSA scan will be scheduled 4 months from the interim UTI.

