#### 10.7.1 Definitions of Treatment Failure

Although treatment will not be provided as part of this observational study protocol, we will characterize the children in the CUTIE Study in terms of the criteria used to define treatment failure in the RIVUR study.

In any participant, the occurrence of two  $F$ UTIs or a total of four  $F/S$ UTIs during the study

period or an interim 12-month scan showing new scarring at a site different from the index APN or worsening scarring evidenced by extension of a preexistent scar seen on the baseline DMSA scan will be classified as a treatment failure. In treatment failure cases where new or worsening scarring is observed on the 12-month DMSA scan, the interim scan may serve as the outcome DMSA scan.

Children whose baseline DMSA scan shows grade 3 or higher scarring in either kidney will have a repeat DMSA performed at the time of any recurrent  $\text{rUTI}$ . If additional renal segment involvement is observed in comparison with the baseline scan, these children will also be categorized as treatment failure and have an outcome DMSA scan at approximately 4 months following the  $\text{rUTI}$ . If no further damage is apparent, they will continue in the study as assigned.

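### The interim-scan criterion for the secondary endpoint 'treatment failure' is stated two ways, and the two versions disagree about a new scar at the site of the index pyelonephritis

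*Protocol*

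**What the plan says.** Section 5.1 names the proportion of children who become treatment failures as a secondary endpoint. Section 5.3.2 gives the purpose, which is to "characterize the children in this ancillary study in terms of the criteria used to define treatment failure in the RIVUR study". The criterion applied to the interim scan appears in two forms.

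**Site-restricted form**
- Abbreviations and Definitions of Terms: "Interim 12-month scan shows new or worsening scarring at a site different from the index APN".
- Section 5.3.2, first paragraph: "an interim 12-month scan showing new scarring at a site different from the index APN".
- MOP 10.7.1, Definitions of Treatment Failure: "period or an interim 12-month scan showing new scarring at a site different from the index APN".

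All three add a second route, worsening shown as enlargement of a scar that was already visible on the baseline scan.

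**Unrestricted form**
- Section 4.5: "If new renal scarring is noted, that child will be considered a treatment failure".
- Section 5.3.2, last paragraph: "Children whose interim 12-month scan shows new or worsening scarring in comparison to a previous scan will be classified as meeting treatment failure criteria".
- The introductory sentence of MOP 10.7 also speaks of new or worsening scarring on follow-up scans without limiting the site.

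The role of the interim scan varies in the same way. In the first paragraph of 5.3.2, "the interim scan may serve as the outcome DMSA scan". Section 4.5 and the last paragraph of 5.3.2 make this mandatory.

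**The concern.** A child cannot be both a failure and a non-failure on the same scan, yet section 5.3.2 alone allows both answers. The case that separates the two rules is the one the protocol's own background leads one to expect, since section 1.1.2 reports that "the sites of new renal scarring correspond exactly to those sites of acute pyelonephritis seen on the initial DMSA renal scans".

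Two things are at stake. The reported proportion with treatment failure depends on which paragraph is applied. The stated purpose of describing these children by the RIVUR criteria also needs a single criterion that matches RIVUR's. The classification is used while the study is running too: under MOP 3.3.1 the coordinating centre tells sites of failure determinations within 2 weeks after the reference radiologists receive the images.

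**Working it through.** No sample-size or error-rate figure is involved. The check is to apply each wording to one test child.

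**Test child.** The baseline scan shows an APN defect and no scar. One febrile UTI recurs in the first 8 months. The 12-month scan shows a new scar only at the index-APN site.

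**Preliminary steps**
1. The interim scan is done. Section 4.5, the Table 1 footnote and MOP 7.4.5.1 all tie it to an interim febrile UTI.
2. The UTI-count route does not apply. It needs two febrile recurrences, or four febrile or symptomatic recurrences in total.
3. The route for children with baseline scarring of grade 3 or higher does not apply, because there is no baseline scar.
4. The extension route does not apply. MOP 3.2.1 classes a defect with preserved contour as APN and one with volume loss as scar, so this child had no baseline scar to extend. For the same reason, the scar is new compared with the baseline scan.

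**Result by location**

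| Text | New scar at index-APN site | New scar elsewhere | Extension of a baseline scar |
|---|---|---|---|
| Abbreviations | not a failure | failure | failure |
| 5.3.2, first paragraph | not a failure | failure | failure |
| MOP 10.7.1 | not a failure | failure | failure |
| 4.5 | failure | failure | not mentioned |
| 5.3.2, last paragraph | failure | failure | failure |
| MOP 10.7, introduction | failure (loosely) | failure | failure |

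The site-restricted texts exclude the test child because neither of their routes is met. They do not say in so many words that such a scar is disregarded. The conflict is confined to the first column.

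**Size per child.** Section 3.2.2 plans 360 children at baseline and 288 at 24 months. One reclassified child moves the proportion by 1/360 = 0.28 points or 1/288 = 0.35 points.

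**Primary outcome.** Section 6.1.2 takes an indicated earlier scan that shows scarring as the primary outcome. The test child therefore counts as scarred whichever failure rule is used.

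**The case against.** The strongest reply is that the documents lean one way. MOP Chapter 10 (October 14, 2008) is later than the protocol (April 23, 2008). Its section headed as the definition of treatment failure repeats the first paragraph of 5.3.2 and leaves out the unrestricted last paragraph. Section 4.5 deals with scan timing and says it uses the RIVUR criteria, so its sentence could be shorthand. This supports the site-restricted wording as the default. It does not settle the matter: the introduction to MOP 10.7 is unrestricted, no text gives one version precedence, and the last paragraph of 5.3.2 has its own comparator and its own consequence.

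A second reply is that scans are read centrally and determinations come from the coordinating centre, so one rule will probably be applied to every child. That stands as far as consistency between sites goes. It does not say which rule is applied, and notices sent during follow-up cannot be undone by a later decision.

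A reader might infer more than the documents support:

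- **A head count.** Combining the 4.6–7.2% reinfection in Table 4 with the 10–35% scarring in section 3.2.3 gives 360 × 0.046 × 0.10 = 1.7 to 360 × 0.072 × 0.35 = 9.1 children. This bounds nothing. Table 4 comes from another trial with long-term follow-up at 6 months. The CUTIE baseline scan may be up to 16 weeks after the index UTI, close to the 4 months used for outcome scans after failure, so some index-site scars may already be present at baseline.
- **A three-way conflict over the outcome scan.** The word 'appropriate' in MOP 10.7.4 is needed. A child who fails on a second febrile UTI after the interim scan still requires a scan 4 months later.
- **Loss of comparability with RIVUR.** The parent protocol is not at hand, so which version matches it cannot be checked.
- **A referral failure.** Section 4.6 lists no interim-scan trigger, but that is a separate matter.

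**Conclusion.** The contradiction holds on the face of the text. For a new scar confined to the index-APN site, the definitions table, the first paragraph of 5.3.2 and MOP 10.7.1 give one answer. Section 4.5 and the last paragraph of 5.3.2 give the other, and the introduction to MOP 10.7 leans the same way.

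The number of children affected cannot be derived from the documents. It is limited to those with an interim febrile UTI who are not already failures by UTI count and whose index-site scar was not already on the baseline scan. It would be wrong to infer that the primary comparison is at risk, because section 6.1.2 protects the any-scar outcome. No hypothesis is attached to the treatment-failure proportion, so the point is minor. The conclusion rests only on reading the paragraphs as written and on the MOP 3.2.1 distinction between APN and scar.

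**What to change.** 1. Adopt one interim-scan criterion, namely the RIVUR definition that section 5.3.2 invokes. Until that is confirmed, default to the site-restricted wording of the definitions table, the first paragraph of 5.3.2 and MOP 10.7.1.
2. State explicitly whether a new scar at the index-APN site counts.
3. Align or delete the unrestricted sentences in section 4.5, the last paragraph of 5.3.2 and the introduction to MOP 10.7.
4. For failures by interim scan only, say throughout that the interim scan will be the outcome scan, and tie this to new or worsening scarring that meets the chosen criterion.
5. Leave 'appropriate' in MOP 10.7.4 for failures by UTI count.

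Do not go further and make every earlier scan that shows any scarring the outcome scan. An unchanged baseline scar could then displace the 24-month scan, which the Table 1 footnote allows to be omitted once an outcome scan exists. Later progression to severe scarring would be missed.

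The cost is wording in the protocol and MOP Chapter 10. No new data are needed: under MOP 3.2.1 the central readers already record the location of affected segments, so either rule can be derived from the readings.
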